5.4 Selection and Timing of Dose for Each Subject

Apixaban: Apixaban is to be dosed at 5 mg by mouth twice daily, except in the case of the criteria listed below in “dose modifications”. The duration of therapy will be at least 30 days. The patient’s physician may determine that anticoagulation therapy should be continued after the study period, based on their examination of the patient at the 30-day post-operative examination.

Apixaban should not be used if a patient has active pathological bleeding.

If a dose of apixaban is not taken at the scheduled time, the dose should be taken as soon as possible on the same day and then continue with twice daily administration as before. The dose should not be doubled to make up for a missed dose.

Apixaban can be taken with or without food.

Apixaban is not recommended in patients with severe hepatic impairment. No dose adjustment is recommended for patients with renal impairment alone, including those with end-stage renal disease (ESRD) maintained on hemodialysis, except nonvalvular atrial fibrillation patients who meet the criteria for dosage adjustment. Patients with ESRD (CrCl <15 mL/min) receiving or not receiving hemodialysis were not studied in clinical efficacy and safety studies with ELIQUIS; therefore, the dosing recommendations are based on pharmacokinetic and pharmacodynamic (anti-Factor Xa activity) data in subjects with ESRD maintained on dialysis.

Warfarin: While patients are hospitalized, warfarin will be dosed daily, with daily INR monitoring per hospital protocol. Daily doses may vary from 0.5mg to 15mg by mouth, as determined by patient specific factors such as patient size, hepatic function, INR, concomitant medications, diet, or other factors. Based on these factors or others not listed, there may also be days in which the patient is prescribed to not get does not receive a dose of warfarin.

After discharge from the hospital, warfarin dosing will be subsequently managed by an anticoagulation clinic, per established protocols. All patients will have a goal INR of 2-3 during the duration of the study. The duration of therapy will be at least 30 days. The patient's physician may determine that anticoagulation therapy should be continued after the study period, based on their examination of the patient at the 30-day post-operative examination.

Warfarin should not be used if a patient has active pathological bleeding.

If a dose of warfarin is not taken at the scheduled time, the dose should be taken as soon as possible on the same day and then continue with daily administration as before, or as recommended by the anticoagulation clinic. The dose should not be doubled to make up for a missed dose.

Warfarin can be taken with or without food, but it is recommended to maintain a consistent intake of vitamin K containing foods.

5.4.1 Dose Modifications

Apixaban: in patients with at least 2 of the following characteristics, age ≥ 80 years, body weight ≤ 60 kg, or serum creatinine ≥ 1.5 mg/dL (133 $\mu\text{mol/L}$), the recommended dose of apixaban is 2.5 mg twice daily.

Warfarin: doses of warfarin will be determined on a daily basis while the patient is in the hospital. After discharge from the hospital, after each INR check, a pharmacist or nurse will contact the patient to communicate the appropriate dosing.

5.4.2 Temporary Discontinuation of Apixaban or Warfarin

Discontinuing anticoagulants, including apixaban or warfarin, for active bleeding, elective surgery, or invasive procedures places patients at an increased risk of thrombosis. Lapses in therapy should be avoided, and if anticoagulation with apixaban and warfarin must be temporarily discontinued for any reason, therapy should be restarted as soon as possible.

5.5 Blinding/Unblinding

Not applicable; study is unblinded.

5.6 Concomitant Treatments

5.6.1 Prohibited and/or Restricted Treatments

Concomitant use of drugs affecting hemostasis increases the risk of bleeding. These include

aspirin and other antiplatelet agents, other anticoagulants, heparin, thrombolytic agents, selective serotonin reuptake inhibitors, serotonin norepinephrine reuptake inhibitors, and nonsteroidal anti-inflammatory drugs (NSAIDs).

5.6.2 Other Restrictions and Precautions

Apixaban should be discontinued at least 48 hours prior to elective surgery or invasive procedures with a moderate or high risk of unacceptable or clinically significant bleeding. Apixaban should be discontinued at least 24 hours prior to elective surgery or invasive procedures with a low risk of bleeding or where the bleeding would be non-critical in location and easily controlled. Bridging anticoagulation during the 24 to 48 hours after stopping apixaban and prior to the intervention is not generally required. Apixaban should be restarted after the surgical or other procedures as soon as adequate hemostasis

has been established. If surgery or invasive procedures cannot be delayed, exercise appropriate caution taking into consideration an increased risk of bleeding. This risk of bleeding should be weighed against the urgency of intervention.

The concomitant use of apixaban or warfarin with antiplatelet agents increases the risk of bleeding. In patients with atrial fibrillation and a condition that warrants mono or dual antiplatelet therapy, a careful assessment of the potential benefits against the potential risks should be made before combining this therapy with apixaban. Patients taking clopidogrel or ticagrelor within 5 days prior to surgery, patients taking prasugrel within 7 days prior to surgery, and patients taking ticlopidine within 10 days prior to surgery, and patients taking clopidogrel, ticagrelor, prasugrel, or ticlopidine during the study period will be excluded from participation in this study.

Use apixaban and warfarin with caution when co-administered with non-steroidal anti-inflammatory drugs (NSAIDs), including aspirin.

5.7 Treatment Compliance

Patient compliance will be monitored during the study. While the patient is hospitalized, we will monitor whether apixaban or warfarin is given as directed by the study coordinator. After the patient has been discharged from the hospital, apixaban compliance will be measured by asking the patient to bring any unused medication to their 30-day post-operative appointment, where remaining tablets will be counted. As 60 tablets will be dispensed to each patient (30-day supply), we use the following formula:

$$[(60 - (\text{\# of remaining tablets})) * 100] / [2 * (\text{days since filled})] = \text{percent compliance.}$$

After hospital discharge, warfarin compliance will be monitored by measuring the time in therapeutic INR range (2-3).

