9	STATISTICAL CONSIDERATIONS.....	38
9.1	Sample Size DeterminationError! Bookmark not defined.	36
9.2	Populations for Analyses	38
9.3	Analyses	36
10	STUDY MANAGEMENT	39
10.1	Compliance with the Protocol.....	39
10.2	Records Retention	40
10.2.1	Records Retention	40
10.2.2	Study Drug Records.....	40
10.3	Destruction of Investigational Product.....	41
11	GLOSSARY OF TERMS.....	42
12	LIST OF ABBREVIATIONS	43
13	REFERENCES.....	44

PROTOCOL SYNOPSIS

Protocol Title:	Apixaban versus warfarin for the management of post-operative atrial fibrillation: a prospective, controlled, randomized pilot study
Site Numbers & Names:	Sanford Medical Center, Fargo, ND
Research Hypothesis:	We hypothesize that there will be no significant differences between apixaban and warfarin anticoagulation strategies for the outcomes of venous thromboembolism/stroke or bleeding events when utilized for new-onset postoperative atrial fibrillation after isolated coronary artery bypass grafting (CABG).
Study Schema: Drugs / Doses / Length of Treatment)	
Patients who develop persistent atrial fibrillation after isolated coronary artery bypass grafting will be identified and randomized to anticoagulation with either warfarin (standard of care) or apixaban.
 
Warfarin will be dosed daily, with International Normalized Ratio (INR) monitoring per hospital protocol. After discharge, warfarin dosing will be managed by the anticoagulation clinic per protocol with a target INR of 2-3.
 
Apixaban will be dosed at 5 mg twice daily, or 2.5 mg twice daily in patients with at least two of the following characteristics: age \geq 80 years, weight \leq 60 kg, or serum creatinine \geq 1.5 mg/dL.
 
Patients will remain on anticoagulation until no longer needed (typically within 30 days of surgery). Study follow-up will be through the patient's 30-day follow-up appointment.

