Study Objectives:	
1) Primary endpoint: freedom from stroke or thromboembolic event will be captured.
 
2) Secondary endpoints: -units of blood given after initiation of anticoagulation medication -total post-operative length of stay -duration from diagnosis of post-operative atrial fibrillation (POAF) to discharge from hospital -time in therapeutic range of INR if on warfarin -patient compliance percentage to apixaban if on apixaban
 
3) Safety assessments: major and minor bleeding events, as defined by the International Society on Thrombosis and Haemostasis, will be captured. Clinical events and blood product utilization will be identified and captured.

Study Design:	
In this open-label, prospective, randomized pilot study, patients who develop atrial fibrillation after isolated coronary artery bypass grafting surgery will be identified. Patients with persistent atrial fibrillation (>12 hours) or recurrent sustained atrial fibrillation (≥ 2 episodes of atrial fibrillation lasting longer than 30 minutes) will be candidates for inclusion. Upon meeting study inclusion and exclusion criteria, and after informed consent, patients will be randomized to either the standard of care (warfarin per protocol) or apixaban arms of the trial. Routine postoperative care after CABG will occur in both groups. Upon discharge, anticoagulation in both groups will be managed by the anticoagulation clinic. Patients will be followed for 30 days after surgery.

Accrual Goal: (Total number of subjects)	56 patients
Accrual Rate: (Number of subjects expected per month)	We anticipate enrolling 2-3 patients per month based on current projections.
FPFV: LPFV: Follow Up: (mm/dd/yy)	FPFV: 9/1/16 LPFV: 12/31/18 Follow up: 30 days per patient Final Report: 3/31/19

Correlative Studies: (PK/PD, etc.)
	
Retrospective analysis conducted at our facility:
 
Anderson E, Johnke K, Leedahl D, Dyke, C. Novel oral anticoagulants vs warfarin for the management of postoperative atrial fibrillation: clinical outcomes and cost analysis. American Journal of Surgery. Volume 210, Issue 6, 1095-1103²

Inclusion Criteria:
	
Patients diagnosed with new-onset persistent or recurrent atrial fibrillation after isolated CABG surgery. Persistent atrial fibrillation is defined as an episode of >12 hours. Recurrent atrial fibrillation is defined as 2 or more episodes of atrial fibrillation lasting longer than 30 minutes.

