2 STUDY OBJECTIVES

2.1 Primary Objective

- 1) Efficacy: Venous thromboembolism or stroke, followed until postoperative day 30.
- 2) Safety: major and minor bleeding events, followed until postoperative day 30, as defined by the International Society on Thrombosis and Haemostasis³
- 3) Clinical relevant non-major bleed.
- 4) Transfusions: units of blood or blood products given after the first dose of anticoagulation.
- 5) Total post-operative length of stay in days, defined as the time the patient leaves the operating room (day 0) until hospital discharge. Length of stay will increase by 1 day with each midnight that is passed.
- 6) Time in therapeutic range of INR, if on warfarin, (eg. 2-3), measured as a percentage and defined for each patient using the Rosendaal equation.
- 7) Patient compliance percentage to apixaban dosing, calculated as a percentage using the following equation
 - a. $(\# \text{ doses prescribed} - \# \text{ of doses not taken and returned to investigator at follow up appointment}) / \# \text{ doses prescribed}$; the follow up visit will occur after anticoagulation prescription has ended.

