4 INVESTIGATIONAL PLAN

4.1 Study Design and Duration

Planned study design: prospective, controlled, randomized pilot study

Screening procedures/study population: Patients will be eligible for screening if they develop atrial fibrillation in the postoperative period that:

1. Persists 12 hours or more.
2. Develop recurrent atrial fibrillation with two or more episodes of persistent AFib of at least 30 minutes duration during the same hospital stay.

Number of subjects per arm: 28

Randomization ratio/method: 1:1, determined in permuted block fashion

Duration of treatment: 30 days of oral anticoagulation therapy. This period will start with the first dose of anticoagulation (either apixaban or warfarin) given in the hospital, and continue until the patient's 30-day post-operative appointment.

Criteria for evaluation:

- Efficacy: systemic thromboembolism or stroke will be assessed retrospectively after the patient has completed the 30-day course of therapy.
 - Events relating to thromboembolism or stroke will be adjudicated using pre-determined definitions by independent committee members that remain blinded to the patient's treatment arm.
- Safety: major bleeding will be as defined by the Society on Thrombosis and Haemostasis, as follows:
 - 1. Fatal bleeding, and/or
 - 2. Symptomatic bleeding that occurs in a critical area or organ, such as intracranial, intraspinal, intraocular, retroperitoneal, pericardial, in a non-operated joint, or intramuscular with compartment syndrome, assessed in consultation with the surgeon, and/or
 - 3. Extrasurgical site bleeding causing a fall in hemoglobin level of 20 g/L (2g/dL) or more, or leading to transfusion of two or more units of whole blood or red cells within 24-48 hours of the bleeding and/or
 - 4. Surgical site bleeding that requires a second intervention – open, arthroscopic, endovascular- or a hemarthrosis of sufficient size as to interfere with rehabilitation by delaying mobilization or delayed wound healing, resulting in prolonged hospitalization or a deep wound infection, and/or
 - 5. Unexpected surgical site bleeding, prolonged and/or sufficiently large to cause hemodynamic instability, as assessed by the surgeon, with a fall in hemoglobin of at least 20 g/L (2g/dL) or transfusion of two or more units of whole blood or red cells within 24 hours of the bleeding.³

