6.4.2 Secondary Assessments

- 1) Units of blood or blood products given after the first dose of anticoagulation.
- 2) Total post-operative length of stay: This will be measured from the date/time of the end of the subject's surgery until the date/time of the patient's discharge from the hospital. This will be measured in hours, to the nearest tenth of an hour.
- 3) Duration from diagnosis of post-operative atrial fibrillation (POAF) to discharge from the hospital: This will be measured from the time of the EKG that is obtained after AFib is noted on telemetry (confirming the diagnosis of AFib), until hospital discharge. This will be measured in hours, to the nearest tenth of an hour.
- 4) Time in therapeutic range of INR, if on warfarin, (eg. 2-3), measured as a percentage and defined for each patient using the Rosendaal equation
- 5) Patient compliance percentage to apixaban: measured by asking the patient to bring any unused medication to their 30-day post-operative appointment, where remaining tablets will be counted. This will be calculated as a percentage using the following

equation: (# doses prescribed - # of doses not taken and returned to investigator at follow up appointment) / # days prescribed.

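### Apixaban compliance, a secondary endpoint, has three conflicting formulas (5.7, 2.1 and 6.4.2) and no rule on which governs; treatment duration is also stated inconsistently

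*Combined protocol and SAP*

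**What the plan says.** The synopsis lists "patient compliance percentage to apixaban if on apixaban" among the secondary endpoints. The formula appears in three places.

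- **Section 5.7:** "As 60 tablets will be dispensed to each patient (30-day supply), we use the following formula". The numerator is 60 minus the tablets remaining, times 100. The denominator is twice the days since filling. Tablets are counted at the 30-day post-operative appointment.
- **Section 2.1, item 7:** "Patient compliance percentage to apixaban dosing, calculated as a percentage using the following equation". Doses prescribed, less those untaken and returned, are divided by doses prescribed. The item adds that "the follow up visit will occur after anticoagulation prescription has ended".
- **Section 6.4.2, item 5:** the numerator matches 2.1, but the expression ends "of doses not taken and returned to investigator at follow up appointment) / # days prescribed".

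Section 9.3 describes how continuous variables are summarised and does not choose among the three.

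Treatment duration is also given in three places.

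- **Synopsis, Study Schema:** "Patients will remain on anticoagulation until no longer needed (typically within 30 days of surgery").
- **Section 4.1:** 30 days of treatment. "This period will start with the first dose of anticoagulation (either apixaban or warfarin) given in the hospital", and it ends at the 30-day post-operative appointment.
- **Section 5.4, both drugs:** "The duration of therapy will be at least 30 days".

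Section 4.2.4 requires a note when a participant who withdraws has not finished the 30-day course.

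**The concern.** The three denominators measure different things, so one tablet count can yield three percentages. With no governing rule, the choice would be made at analysis, possibly after the counts have been seen. The protocol offers this pilot as a reference for later studies, so an adherence figure that depends on the section followed is of limited use.

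Two further matters follow. First, the 5.7 denominator runs to the tablet count whatever happens to the prescription. The protocol foresees earlier stops ordered by a clinician (synopsis, 4.2.4, 6.1) and temporary holds (5.4.2, 5.6.2). Days without prescribed drug would then count as missed doses. Second, because duration is stated in three ways, it is unclear which stops fall short of the 30-day course that 4.2.4 refers to.

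**Working it through.** **Inputs from the protocol.** One tablet twice daily (5.4). 60 tablets dispensed as a 30-day supply (5.7), which reproduces: 2 × 30 = 60. Dispensing at hospital discharge (schedule in 6.1). Count at the 30-day post-operative visit (5.7). Therapy usually lasts 3 to 4 weeks (Introduction). Atrial fibrillation is most common within four days of surgery and peaks on postoperative day (POD) 2 (1.1).

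**Assumed, because the protocol gives no figures.** Discharge and fill on POD 5 to 7, first dose on POD 2 to 5, count on POD 30 or POD 35, all unused tablets returned. Unless stated otherwise, doses prescribed = 60 and days prescribed = 30.

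**Formulas.** Let D be the fill day, V the count day and T the tablets taken.

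- 5.7: 100 × T / [2 × (V − D)]
- 2.1: 100 × T / 60
- 6.4.2: 100 × T / 30

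**Patients who take every prescribed dose while supply lasts:**

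| Case | 5.7 | 2.1 | 6.4.2 |
|---|---|---|---|
| All 60 taken, counted 30 days after filling | 60/60 = 100% | 60/60 = 100% | 60/30 = 200% |
| Filled POD 6, counted POD 30 (48 taken, 12 left) | 48/48 = 100% | 48/60 = 80% | 48/30 = 160% |
| All 60 taken, counted 33 days after filling | 60/66 = 90.9% | 60/60 = 100% | 60/30 = 200% |
| Filled POD 7, directed stop POD 23, counted POD 30 (32 taken, 28 left) | 32/46 = 69.6% | 32/60 = 53.3% | 32/30 = 106.7% |

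**Spare tablets under 2.1.** Because the supply is issued at discharge, a POD 30 count comes fewer than 30 days after filling, and tablets are left over even with perfect use. For fills on POD 5 to 7, 2.1 gives 50/60 = 83.3% down to 46/60 = 76.7%. With a POD 35 count it gives 60/60 = 100% down to 56/60 = 93.3%. For the POD 6 fill and POD 30 count, reading doses prescribed as the 48 doses due while still subtracting the 12 returned tablets gives 36/48 = 75%.

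**Directed stop under 5.7.** With a stop on day S, a fully adherent patient scores 100 × (S − D)/(V − D), which is below 100% whenever S precedes V. Taking S as 21 or 28 days after the first dose:

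- Count on POD 30: lowest (23 − 7)/(30 − 7) = 16/23 = 69.6%. With four weeks of therapy the stop falls on POD 30 or later, so there is no shortfall.
- Count on POD 35: lowest 16/28 = 57.1%, highest (33 − 5)/(35 − 5) = 28/30 = 93.3%.

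**Directed hold under 5.7.** Section 5.6.2 has apixaban stopped at least 48 hours before higher-risk procedures. Two days off in the 24 from POD 6 to POD 30 gives 44/48 = 91.7%.

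**Duration.** A first dose on POD 2 to 4 and a visit on POD 30 give 28 to 26 days. Under those assumptions the period in 4.1 falls short of its own 30 days and of the minimum in 5.4. The synopsis sets no minimum.

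**The case against.** Much of the case on the other side is sound.

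- **6.4.2 is probably a typing slip.** It repeats 2.1 with days in place of doses and calls the result a percentage. A value of 200% would expose itself. This stands, but correcting the word still leaves 2.1 and 5.7. With 60 doses prescribed, those two agree for anyone who took tablets only when the count falls exactly 30 days after filling.
- **2.1 has a benign reading.** If doses prescribed means doses due up to any stop, and only missed doses are subtracted, it gives 100% for every adherent patient. The text does not say so: spare tablets are also untaken and returned.
- **A directed stop is not hidden.** A reader might infer that ordered stops would pass silently as poor adherence. Sections 4.2.4 and 6.1 require the reason for withdrawal or discontinuation to be documented, so the information exists; it is just not linked to the formula. Whether a stop should shorten the denominator is also partly a matter of convention, adherence versus persistence.
- **The directed-stop figures rest on assumed days.** More extreme examples are easy to build, such as a stop on POD 21. But three weeks from a first dose on POD 2 ends on POD 23, so such an example lies outside the range used here.
- **The visit-timing conflict is thin.** Section 2.1 puts the visit after the prescription ends and 4.1 runs treatment up to the visit; the two can nearly coincide.

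**Conclusion.** The protocol is wrong as written on this endpoint, and the point is minor. At least two of the three formulas misstate compliance for a fully adherent patient: 80% under 2.1 and 160% under 6.4.2, against 100% under 5.7, for a POD 6 fill and POD 30 count. The 200% from 6.4.2 for 60 tablets over 30 days needs only protocol figures plus reading days prescribed as 30. The 80% also rests on assumed fill and count days and on doses prescribed meaning the 60 dispensed.

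Section 5.7 is the best base. Its weaknesses are secondary: it has no allowance for directed stops or holds, and no cap at the 60 tablets supplied. The stop result holds algebraically, but its size depends on assumed days, and the documents do not show how often it would arise.

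Two stronger inferences are not supported. Because 2.1 lists compliance under its primary objective, a reader might think that a primary result is at risk. The synopsis and 6.4.2 make it secondary, it is measured in the apixaban arm only (28 patients), and the stroke and thromboembolism comparison does not use it. A reader might also infer from the duration conflict that one particular rule is correct. The documents do not settle that, and a minimum length of anticoagulation is a clinical decision. The conflict itself is real and bears on the non-completion note.

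**What to change.** **One formula, in 5.7, cited from 2.1 item 7 and 6.4.2 item 5, whose own formulas are deleted:**

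Compliance (%) = 100 × (60 − tablets remaining) / doses due, where doses due is the smaller of (i) 60 and (ii) 2 × (days from filling to the earlier of the tablet count and any physician-directed permanent stop, minus days of physician-directed temporary hold). Patient-initiated stops keep the full denominator.

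Check on the cases above:

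- POD 6 fill, POD 30 count: 48/48 = 100%.
- All 60 taken, counted at 33 days: 60/60 = 100%.
- POD 7 fill, directed stop POD 23: 32/32 = 100%.
- Two-day directed hold: 44/44 = 100%.
- Patient-initiated stop on POD 23, filled POD 7, counted POD 30: 32/46 = 69.6%, as intended.

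One limit remains. When the count comes more than 30 days after filling, a late-taken tablet cannot be told from one taken on time.

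**Duration.** State one rule in the synopsis, 4.1 and 5.4, for both arms, and tie the 4.2.4 note to it. The investigators should choose whether to keep the 30-day minimum, end at the visit, or stop when no longer needed. If the minimum stays, a first dose on POD 2 to 4 carries treatment to POD 32 to 34, past a POD 30 visit, and 4.1 must allow for that.

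**Cost.** Wording, plus the dates of directed stops and holds as added data items; the reason for stopping is already required. The formula change needs no new visit, supply or sample size and leaves clinicians free to stop treatment. The duration choice needs clinical agreement.
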